IFN	interferon
IFTA	Interstitial fibrosis/tubular atrophy
iIFTA	Banff lesion score interstitial inflammation in areas of Interstitial fibrosis/tubular atrophy
IMP	Investigational Medicinal Product
IVIg	Intravenous immunoglobulins
KRUK	Kidney Research UK
MFI	Mean Fluorescence Index
MVI	Microcirculation inflammation
MHRA	Medicines and Healthcare products Regulatory Agency
NK	Natural killer
NHSBT	NHS Blood and Transplant registry

PEX	Plasma exchange
PIS	Participant Information Sheet
ptc score	Banff Lesion score Peritubular capillaritis
R&D	Research and Development
REC	Research Ethics Committee
RCT	Randomised controlled trial
RRT	Renal Replacement Therapy
SOC	Standard of Care
SOCR	Standard of Care plus Rituximab
t	Banff lesion score interstitial inflammation in non-scarred areas
TAR:GET-1	Transplant Antibody Mediated Rejection: Guiding Effective Treatments clinical trial
TCMR	T-cell mediated rejection
ti	Banff lesion score interstitial inflammation in total cortex
TMG	Trial Management Group
TSC	Trial Steering Committee
UPCR	Urinary protein:creatinine ratio
v score	Banff lesion score Arterial inflammation

KEYWORDS

Kidney transplant, antibody-mediated rejection, transplant biopsy, gene expression analysis, donor-specific antibody, B cells

STUDY SUMMARY

Title of Study: Mechanistic Evaluation of Treatments for Acute Antibody-Mediated Rejection of the Kidney Transplant
Design: Prospective observational study of patients enrolled in TAR:GET-1
Objectives: TAR-GET-1 (starting in 2019) is a multi-centre UK clinical trial that will compare standard of care (SOC) treatment of Acute Antibody-Mediated Rejection of the Kidney Transplant (AAMR) to standard of care plus rituximab (SOCR). This trial presents a rare opportunity to investigate the mechanisms of action of treatments (including rituximab) in AAMR. The rationale for using rituximab is the depletion of CD20-positive precursors to antibody-producing cells. However, rituximab has effects on other B cell subtypes and not all studies have shown antibody level reductions. Furthermore, AAMR is a heterogeneous disease, as defined by variability in mechanistic markers of AAMR in blood (B cell and antibody characteristics) and in transplant biopsies (histological features and gene expression). The objectives of this study are: 
• To investigate how treatment with rituximab affects these mechanistic markers, by comparing SOC to SOCR• To predict treatment benefit early, by analysing the effect of treatment on the mechanistic markers
Methodology: In patients enrolled in TAR:GET-1 (n=170), we will analyse mechanistic markers with established proof of concept (B cell and antibody characteristics, histological and transcriptional markers in the biopsy) at baseline and on follow-up, making use of clinical data, surplus diagnostic material from TAR:GET-1, and material from optional extra blood samples for research taken as part of TAR:GET-1, at 3,6 and 12 months. We will also offer an optional protocol biopsy at 6 months post treatment. Differences pre- and post-treatment will be analysed comparing SOC and SOCR. We will use mediation analysis models to decompose total effect of treatment effect on graft loss at 4 years (primary end point) into an indirect effect, which measures how much of the effect acts through the intermediate variable(s), and a residual direct effect.
Number of Subjects and Study populations: 170 subjects enrolled in TAR:GET-1
Outcome measures: same as primary outcome of TAR:GET-1 (graft loss at 4 years after initiation of treatment)
Inclusion Criteria: All patients enrolled in TAR:GET-1 Signed informed consent prior to any study specific procedures.

Exclusion Criteria:

None

Investigational Product: N/A**Duration of study:** 8 years (duration is dictated by the need for primary outcome of TAR-GET-1 to be reached)**Statistical Methods:**

Data from this research project will be merged and linked with data from the TAR:GET-1 clinical trial by the statistician team.

Descriptive data

This will include description of all the biological characteristics analysed in 2 populations (rituximab + SOC and SOC) at baseline and at all follow-up time points. Summary statistics (mean, median, SD, range for continuous variables, and frequency tables for categorical variables) will be reported broken down by treatment, with exploratory figures (box-and-whisker plots for continuous, and stacked bar-charts for categorical).

Outcome analysis

Appropriate measures of differences between treatment groups will be estimated with point estimates, 95% confidence intervals, and p-values. Depending on the type of variable (continuous, categorical, time-to-event), regression techniques (linear, logistic, cox) and transformation of the endpoints will be considered.

Differences in characteristics comparing pre- to post-treatment samples at sequential time points will be analysed comparing the 2 groups of patients (SOCR versus SOC) using r mixed effect models repeat measurement techniques.

Mediation analysis, a special case of regression analysis, will be used to document that the treatment effects a change in the biomarker. We will use mediation analysis models to decompose total effect of treatment effect on graft loss into an indirect effect, which measures how much of the effect acts through the intermediate variable(s), and a residual direct effect. All the mediation analyses will be based on the Intention-to-Treat principle. We will fit the same form of outcome models as for the efficacy analyses, including the mediator as a covariate. We will use the mediation package within R which was developed specifically to make valid causal inference in explanatory analyses of the mechanisms of treatment-induced change in clinical outcomes in randomised clinical trials. All estimates of treatment differences will be summarised using effect size estimates and 95% confidence intervals (Dunn 2013). Collaborator for mediation analysis: [name], Professor of Statistical Methods for Medicine, UCL.

1. INTRODUCTION

1.1 BACKGROUND

Impact of Antibody-mediated rejection (AMR) on kidney allograft survival

Kidney transplantation is the treatment of choice for patients with end stage kidney disease resulting in improved health, patient survival and quality of life (Gibbons 2016), as well as health economic benefit in comparison to remaining on dialysis (Baboolal 2008). The UK adult prevalence of renal replacement therapy (RRT) is 962 per million population (pmp)(Renal Registry Report 2017). The UK prevalent transplant population in 2016 was 34,286 (Pyart 2018).

The use of current immunosuppression regimens, along with careful immunological selection of transplant recipients, has improved short term renal allograft survival. However long term allograft survival remains unchanged, with the average lifespan of a kidney transplant up to 15 years at most (Meier-Kriesche 2004). Rejection is an important cause of transplant failure, mostly due to chronic AMR (Loupy 2018).

TAR:GET-1 : a clinical trial for the treatment of AAMR

There is currently no high quality evidence from randomised trials to guide treatment of acute AMR (Velidedeoglu 2018). Clinical trials of existing and new drugs for AMR are a recognised priority for patients and researchers in the transplant community, as noted in the NIHR James Lind Alliance priority setting partnership 2016 (www.transplantpsp.org). The recently published UK Renal Research Strategy document (drafted following extensive patient and public consultation) similarly highlights the complete lack of evidence in treating AAMR and identifies this as a key research priority (www.kidneyresearchuk.org/research/ukkrcc). This need for trials in acute AMR is recognised globally; the US FDA convened workshops aimed at assessing AMR treatments during 2010 and 2017 (Velidedeoglu 2018).

The TAR:GET-1 trial is due to start in early 2019. This trial provides a time-limited opportunity to carry out research into the mechanisms of action of rituximab in acute AMR (AAMR), which are poorly understood, using samples accrued in a randomised controlled trial, with uniform treatment and follow-up.

MOT-AMR : a time-limited opportunity to advance our understanding of the mechanisms under-pinning AMR and how treatments affect them

Kidney transplantation occurs most frequently across a degree of HLA incompatibility. Despite immunosuppression, this HLA disparity frequently leads to B cell activation and production of donor-specific antibodies (DSA), some of which cause antibody-mediated injury to the graft. In addition, depending on local protocols, some recipients already have antibodies against the HLA epitopes of the graft before transplantation (sensitised patients with pre-formed antibodies and positive cross match transplantation) (Lefaucheur 2008).

A diagnosis of AAMR rests on the identification of serum DSA plus the presence in the graft biopsy of specific histological and/or transcriptional features related to the effect of antibody on the graft endothelium (Haas 2018a). The biopsy is necessary to prove that graft dysfunction is being caused by the antibody, as not all DSA cause injury. These diagnostic features are predictive of outcome and are used to enrol patients in clinical trials of AAMR. However, AAMR is a heterogeneous disease, as defined by variability in mechanistic markers of AAMR in blood (B cell and antibody characteristics) and in transplant biopsies (histological features and gene expression). In addition, individual variations in genes

Mechanistic Evaluation of Treatments for Acute Antibody-Mediated Rejection of the Kidney Transplant (M.O.T. AMR) – Version 1.4 27/05/2020

involved in co-ordinating the patient's immune response (e.g. Fc gamma receptors) may influence B cell activation (Steri 2017; Andres Floto 2005).

Rituximab is a chimeric murine-human monoclonal antibody directed against the B-cell surface molecule CD20, which depletes B cells with CD20 on their surface. Use of Rituximab in AMR has been developed on the basis that, following a primary challenge, in the presence of rituximab, B cells would be prevented from undergoing proliferation and would undergo apoptosis via complement-mediated and complement independent mechanisms. This may lead to reduction in antibody titre, and reduced antibody-mediated graft injury (Fehr 2009; Vo 2010). However, on the one hand, the effects of rituximab on the immune system are wider ranging, and on the other hand, the limited studies that have investigated response to rituximab have not consistently demonstrated the expected effect (Gudbrandsdottir 2018, Cornec 2016, Ehrenstein 2016, Ikemiyagi 2017, Pallier 2010). Investigations of the transcriptional profile of peripheral blood B cells and B cell regulatory potential show promise in elucidating the link between B cell phenotype and AMR (Clatworthy 2009 and 2014, Banham 2018).

This research will investigate the effect of rituximab along the pathophysiological pathway of development of AMR: changes in B cell characteristics; changes in anti-donor antibody titres and characteristics; and changes in histological and transcriptional evidence of AMR in the graft tissue. A better understanding of the mechanisms of rituximab in comparison to standard of care will provide evidence for its use in AAMR, and may provide information on the characteristics of patients with AAMR that are likely to respond to the drug, and information on how to measure response to the drug. These are vital to improving an effective and efficient use of drugs in treating AAMR.

1.2 RATIONALE FOR CURRENT STUDY

This research proposal is a bolt-on mechanistic study, affiliated to an NIHR HTA/Kidney Research UK-funded UK multicentre randomised controlled trial to assess the safety and efficacy of rituximab + standard of care (SOCR) compared with SOC in treating acute antibody-mediated rejection (AAMR) in kidney transplantation (TAR:GET-1)(Transplant Antibody Mediated Rejection: Guiding Effective Treatments; ISRCTN pending, EudraCT ref 2018-002882-20). This phase 3, 2-arm, open-label randomised controlled trial will enrol patients with biopsy-proven AAMR and randomise them to SOCR versus SOC (85 patients in each arm). The trial is scheduled to start in Spring 2019, and patients will be recruited over 40 months, then followed up for 4 years post treatment (follow up complete late 2026). The primary objective is efficacy, with graft survival at 4 years the primary end point.

Analysis of B cell, antibody and biopsy characteristics of patients enrolled in TAR:GET-1 will address several questions:

1) Which patients with a diagnosis of AMR require additional immunosuppression?

It is recognised that AAMR is a heterogeneous disease, and there is evidence that severity of the individual diagnostic features at presentation (HLA antibody strength, biopsy Banff scores) is associated with outcome. Novel parameters not yet used in routine diagnosis also hold promise in increasing diagnostic accuracy and directing treatment; these include complement-activating ability of DSA (Viglietti 2017, Sicard 2015, Bouquegneau 2018), the AAMR-related gene expression signature level (Loupy 2014, Halloran 2016), and B cell characteristics (genomic, transcriptional and functional). The data from past investigations is contradictory, most often derived from retrospective observational studies without uniform

Mechanistic Evaluation of Treatments for Acute Antibody-Mediated Rejection of the Kidney Transplant (M.O.T. AMR) – Version 1.4 27/05/2020

follow-up and treatment, and often lacks robust multivariate analyses. There is insufficiently robust evidence to promote risk stratification and selection of patients for additional treatment.

2) How can we tell if treatment is working?

Serial measurements of the strength of DSA and severity of biopsy features have been used to describe the natural history of AAMR and to determine response to treatments, including rituximab. There is evidence in the literature that treatment of AAMR may reduce antibody strength and/or affect complement-activating ability (Cioni 2018, Viglietti 2018b, Bailly 2018, Lefaucheur 2018) and may have a positive effect on biopsy scores (Viglietti 2018a, Sautenet 2016, Eskandary 2018, Choi 2017) or transcript levels (Eskandary 2018, Lefaucheur 2018). Immunosuppression can induce changes in B cell gene expression and functional profile (Banham 2018). However, the evidence is inconclusive and in places contradictory, and has not been validated in the context of randomised controlled trials. Therefore, serial measurements are not yet used to guide treatment decisions.

3) The need for surrogate endpoints for clinical trials in AMR

Given that the end point for trials in AAMR (graft loss) is remote, development of surrogate end points for AAMR trials is a priority (Velidedeoglu 2018). Longitudinal assessment of biomarkers in patients with AAMR has been shown to assist in outcome prediction, but here again data is limited (Viglietti 2018a). This project provides an opportunity to investigate potential surrogate markers of outcome.

This MOT-AMR research proposal has 2 hypotheses:

Hypothesis 1: AMR is a heterogeneous disease, with outcome and response to treatment accurately predicted by mechanistic biomarkers (B cell, DSA and biopsy features) at baseline, including more recently characterised complement-activating ability of DSA and AAMR gene expression biopsy signature.

Hypothesis 2: Although the clinical endpoint of TAR:GET-1 is graft loss, effective AAMR therapy will be reflected in changes in mechanistic features in serum and in biopsies. In the case of treatment with rituximab, this is achieved through favourable changes in B cell characteristics.

2. STUDY OBJECTIVES

The primary objective is to investigate the mechanisms of treatments including rituximab in AAMR, by measuring the effect of SOCR versus SOC on mechanistic markers of AMR (B cell characteristics, antibody characteristics, end organ damage assessed by histology and transcript analysis)

The secondary objective is to predict treatment benefit early, by decomposing the effect of treatment on graft loss at 4 years (primary end point) into an indirect effect, which measures how much of the effect acts through the changes in mechanistic markers, and a residual direct effect.

3. STUDY DESIGN

Patient Cohort

This is a prospective cohort study using samples from all patients enrolled in the TAR:GET-1 (170 patients, 85 in each arm). The TAR:GET-1 trial will recruit patients starting in June 2019, over a period of 4 years, and patient will be followed up with further biological samples taken over a further period of 4 years. This will need to be analysed for which we estimate a further 2 years. The total duration of the study is therefore 10 years starting June 2019.

We aim to collect all samples from each patient to maximise the information obtained, whilst incurring negligible extra risk to the study participants.

Some of the samples are already obtained as part of the TAR:GET-1 protocol and we will use left over material to carry out analyses.

Some of the samples are not routinely obtained for TAR:GET-1 enrolment, but the TAR:GET-1 protocol and consent process covers their (optional) collection.

The only extra samples that requires a new consent process as part of M.O.T.-AMR is an optional post-treatment protocol biopsy.

The study aim is to be a comprehensive assessment of antibody-mediated rejection biomarkers pre- and post-treatment, but has below been artificially divided into Parts 1 and 2, Part 1 being funded by Imperial BRC, Cambridge BRC and NIHR EME (funding secured) whereas applications for funding for Part 2 are in process. A funding approval letter will be provided to the Sponsor and REC committee prior to commencing any element of part 2 of the study, and will specify which further specific elements of the study have received funding approval.

Samples taken as part of TAR:GET-1:

Patients enrolled in TAR:GET-1 will have a number of samples taken, and consent for enrolment in TAR:GET-1 includes agreement to the use of extra material left after diagnosis for research. We will therefore be able to access in 100% of patients enrolled in TAR:GET-1:

- Enrolment biopsy material
- Serum samples taken for DSA measurements
- Post-treatment indication biopsies taken as part of routine clinical care.

TAR:GET-1 is already assessing DSA MFI, DSA target and B lymphocyte numbers at baseline and 3 months post-treatment. In addition to these, M.O.T.-AMR will analyse in left over material from these routine samples:

1) Serum DSA characteristics at an extra timepoint (costs not covered in TAR:GET-1; 1 year), plus more detailed DSA analyses at all 3 timepoints including not only anti-HLA antibodies (IgG subtype, complement-activating ability) but also non-HLA antibodies;

2) Biopsy Banff histological scores (Roufosse 2018); The following data will be obtained for each biopsy:

- Total number of glomeruli
- Number of glomeruli with global sclerosis
- Number of glomeruli with segmental sclerosis
- Number of scorable glomeruli (excluding those with global/segmental sclerosis and ischaemic changes)
- Percentage of cortical scarring [tubular atrophy, interstitial fibrosis]

Mechanistic Evaluation of Treatments for Acute Antibody-Mediated Rejection of the Kidney Transplant (M.O.T. AMR) – Version 1.4 27/05/2020

- Full Banff lesion scores (t,i,ti,v,g,ptc,ct,ci,cg,cv,ah, C4d) and the microcirculation inflammation score (MI=g+ptc)
- Extent of peritubular capillary inflammation (% of cortex)
- Number of glomeruli with glomerulitis
- Number of glomeruli with capillary wall double contours
- Result of SV40 immunostain (positive/negative)
- Banff Classification for Allograft Pathology diagnostic category(ies) and subcategory(ies)
- Ultrastructural features: presence and distribution of electron dense deposits; extent of foot process effacement; extent of glomerular and peritubular capillary basement membrane multilayering; extent of ultrastructural endothelial activation; presence of tubuloreticular inclusions
- If performed, immunofluorescence staining pattern for IgG, IgA, IgM, C3, C1q, kappa light chain and lambda light chain;

3) Biopsy gene expression will be assessed using Nanostring nCounter technology (Adam 2016; Dominy 2019); this will include the AMR-gene expression signature (Haas 2018), and a B cell signature. As literature is evolving and it is possible to test for hundreds of genes on the same sample, the list of genes to be studied may evolve.

4) Serum BAFF (B cell activating factor) levels

Funding:

Part 1 (covered by Imperial BRC, Cambridge BRC and NIHR EME 129029): Shipping of the samples, 1), 2) and 3).

Part 2: 1) and 4); we will be applying to other funding sources, including Kidney Research UK and local NHS Trust research charity funds.

Optional samples covered by TAR:GET-1 consent process

The additional samples are optional and M.O.T.-AMR is not dependent on them being obtained. As part of TAR:GET-1, patients will be offered the option of contributing extra tubes of blood at baseline, 3 months, 6 months and 1 year, and may decline any of them or all of them.

The extra samples will be: 1) lithium heparin tubes for PBMC isolation in order to carry out B cell immunophenotyping (flow cytometry); peripheral blood B cell stimulation assay (stimulation assay utilising intracellular staining for IL10 and IL6 and deriving a ratio to study regulatory potential of peripheral blood B cells)(Banham 2018)(extra tube of blood at 3 time points, fresh sample needed); and DNA analysis; and 2) PAXgene tubes for peripheral blood transcriptomics (whole blood transcriptomic analysis)(extra tube of blood at 3 time points).

Samples for 1) need to be shipped rapidly and we do not expect to take these samples until funding is secured, so estimate 50% of patients will contribute these, in the later stages of the trial. Samples for 2) can be frozen and batch-shipped so we expect them to be obtained in about 90% of patients.

Funding:

Part 1: Funding for taking and shipping of the PAXgene tubes will be covered by Cambridge BRC.

Part 2: We are applying for funding for the lithium heparin tube samples, and their collection will not be started until funding is secured. We are also applying for funding for the transcript analysis and DNA analysis.

Mechanistic Evaluation of Treatments for Acute Antibody-Mediated Rejection of the Kidney Transplant (M.O.T. AMR) – Version 1.4 27/05/2020

Optional post-treatment renal transplant protocol biopsy

Specifically for M.O.T-AMR, patients enrolled in TAR:GET-1 will be offered an optional protocol biopsy at 6 months post-treatment. This additional sample is optional and M.O.T.-AMR is not dependent on it being obtained. This protocol biopsy will be carried out in the local centre, by the local clinical team. A post-treatment protocol biopsy is a biopsy taken in a patient with stable transplant function and no indication for a biopsy to be taken. The literature suggests that this a useful tool for monitoring response to treatment (Viglietti 2018a), but strong evidence from randomised controlled trials such as TAR:GET-1 is lacking for its routine introduction into clinical care and therefore, in most centres a post-treatment protocol biopsy is not offered to patients. The protocol biopsy will be collected for research and costed as research. Biopsy results on these protocol biopsies will be made available to the clinicians if any unexpected findings that need to be acted upon for patient benefit are noted. We will carry out the same histological and transcriptional investigations on these biopsies as for the enrolment and indication biopsies. A conservative estimate of protocol biopsy acceptance is 50%, based on our local experience (85 samples), and this is the number of samples we aim to achieve.

Funding:

Part 2: Funding for taking these biopsies is covered by NIHR EME 129029. Shipping and analysis will be partly covered by Imperial BRC.

This table illustrates how visits and samples in TAR:GET-1 will be used for investigations in M.O.T.-AMR. The additional samples needed for M.O.T.-AMR are in italic.

TAR:GET-1 trial visits	Baseline	Unscheduled	Visit 3 (month 3)	Visit 4 (month 6)	Visit 5 (month 12)
Biopsy histology and gene expression analysis	Use leftover sample	Indication biopsy for graft dysfunction: Use leftover samples		Optional protocol biopsy	
Serum DSA characteristics and BAFF	Use leftover sample		Use leftover sample		Use leftover sample
B cell characteristics and Peripheral blood transcriptomics	2 extra blood tubes		2 extra blood tubes	2 extra blood tubes	2 extra blood tubes

Sample storage:

Central storage will be at Imperial College. Samples will be dispatched to other centres for processing. Samples will be stored at Imperial College and Cambridge University, using -80C freezers for frozen samples and room temperature storage for slides and paraffin blocks. For B cell immunophenotyping, we will have samples sent fresh to Birmingham University for PBMC preparation, immediate flow cytometry, and storage of left over frozen PBMC. Samples may also be stored at Viapath.

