7. STATISTICS AND DATA ANALYSIS

The patient cohort size is dictated by TAR:GET-1: 170 patients, 85 in each arm. Under plausible modelling assumptions, for any biomarker that is on the mechanistic pathway between treatment and primary outcome, the power of the main study (90%) will be matched or exceeded when comparing the mean biomarker values between treatment groups. The mediation analysis will estimate for each biomarker the influence on allograft survival rate per unit change in biomarker, above and beyond, the direct effect of treatment. This will decompose the overall, marginal, treatment effect into a proportion attributable to a mechanism via the biomarker, and the complement attributable to direct effects, or other mechanisms. A similar multivariable analysis will proceed to estimate the mediation effects of multiple biomarkers acting in parallel, as an exploratory analysis using variable selection methods to control for over-fitting.

Data from this research project will be merged and linked with data from the TAR:GET-1 clinical trial by the statistician team.

Descriptive data

Mechanistic Evaluation of Treatments for Acute Antibody-Mediated Rejection of the Kidney Transplant (M.O.T. AMR) – Version 1.4 27/05/2020

This will include description of all the biological characteristics analysed in 2 populations (rituximab + SOC and SOC) at baseline and at all follow-up time points. Summary statistics (mean, median, SD, range for continuous variables, and frequency tables for categorical variables) will be reported broken down by treatment, with exploratory figures (box-and-whisker plots for continuous, and stacked bar-charts for categorical).

Outcome analysis

Appropriate measures of differences between treatment groups will be estimated with point estimates, 95% confidence intervals, and p-values. Depending on the type of variable (continuous, categorical, time-to-event), regression techniques (linear, logistic, cox) and transformation of the endpoints will be considered.

Differences in characteristics comparing pre- to post-treatment samples at sequential time points will be analysed comparing the 2 groups of patients (SOCR versus SOC) using mixed effect models repeat measurement techniques.

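### With B cells removed in one arm only, the IL10/IL6 ratio and B-lineage blood transcripts cannot be read as a change in per-cell state

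*Protocol*

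**What the plan says.** The Study Summary gives the reason for the drug: "The rationale for using rituximab is the depletion of CD20-positive precursors to antibody-producing cells". Section 1.1 describes rituximab as an antibody "which depletes B cells with CD20 on their surface". It is given in SOCR and not in SOC.

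The primary objective (Section 2) compares B-cell, antibody and biopsy markers between SOCR and SOC. Hypothesis 2 (Section 1.2) holds that rituximab works by improving B-cell features.

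Section 3, under the optional samples, says that "patients will be offered the option of contributing extra tubes of blood at baseline, 3 months, 6 months and 1 year". One tube serves flow-cytometric immunophenotyping and a "stimulation assay utilising intracellular staining for IL10 and IL6 and deriving a ratio to study regulatory potential of peripheral blood B cells". The other is described as "PAXgene tubes for peripheral blood transcriptomics (whole blood transcriptomic analysis", that is, bulk blood and not sorted B cells.

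On cell number, Section 3 says only that "TAR:GET-1 is already assessing DSA MFI, DSA target and B lymphocyte numbers at baseline and 3 months post-treatment".

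Section 7 says that pre- to post-treatment differences "will be analysed comparing the 2 groups of patients (SOCR versus SOC) using mixed effect models repeat measurement techniques". It adds: "The mediation analysis will estimate for each biomarker the influence on allograft survival rate per unit change in biomarker". The mediator enters the outcome model as a covariate.

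**The concern.** The drug that defines one arm acts on the cells in which some of the markers are measured. This has three consequences.

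- **Ratio and subset percentages.** They have no value in a patient without B cells and a poor one in a patient with few. Whether a sample is evaluable is decided after randomisation, by the drug, in one arm. The contrast then sets surviving or returning cells in SOCR against an unselected population in SOC.
- **Whole-blood transcripts.** A fall in B-lineage RNA in SOCR is expected from cell loss, even if every remaining cell is unchanged.
- **Mediation.** A marker with no value in a depleted patient has no unit change to act through. For a marker that arm nearly determines, direct and indirect effects can be separated only by extrapolation.

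At stake is how the B-cell part of Hypothesis 2 is interpreted. A reported shift in regulatory potential or transcript profile could be cell loss, or selection of evaluable samples, under another name.

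**Working it through.** **Inputs from the protocol.** 170 patients, 85 per arm (Section 7). Expected uptake is 50% for the lithium heparin (B-cell) tube and about 90% for the PAXgene tube (Section 3). B-lymphocyte numbers are named at baseline and month 3 only.

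**Inputs not in the protocol, so assumed.** Depth and duration of depletion, number of B cells acquired, share of a transcript that comes from B cells, and separation of the arms on the count.

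**The plan's own figures.** 0.50 × 170 = 85 patients, 42.5 per arm; 0.90 × 170 = 153 patients, 76.5 per arm. These count patients who give tubes, not tubes that yield a value. The 90% power quoted for any biomarker on the pathway cannot be reproduced, because no alpha, effect size or SD is given. Solving backwards with two-sided 5% alpha, 85 per arm has 90% power for a standardised difference of (1.960 + 1.282) × √(2/85) = 0.497.

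**Step 1: whole blood with no per-cell change.** If a share s of a transcript comes from B cells and a share d of B cells is lost, the apparent log2 fold change is log2(1 − s·d).

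| B-cell share s | d = 50% | d = 90% | d = 99% |
|---|---|---|---|
| 100% | -1.00 | -3.32 | -6.64 |
| 50% | -0.42 | -0.86 | -0.99 |
| 10% | -0.07 | -0.14 | -0.15 |

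The effect is large for B-lineage transcripts and close to nil for the rest.

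**Step 2: precision of the ratio.** Assume 5,000 B cells acquired without depletion, 2% IL10-positive and 10% IL6-positive. With N cells, the SD of the log ratio is √[0.98/(0.02N) + 0.90/(0.10N)].

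- No depletion, N = 5,000: √(0.0098 + 0.0018) = 0.11.
- 90% depletion, N = 500: 0.34.
- 99% depletion, N = 50: 1.08, and 0.98^50 = 36% of samples have no IL10-positive cell.

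Under these inputs the ratio is usable at 90% depletion and often undefined at 99%.

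**Step 3: composition.** Assume a 10% subset with ratio 0.6 and a 90% subset with ratio 0.1, with equal IL6 positivity. The starting average is 0.1 × 0.6 + 0.9 × 0.1 = 0.15.

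- Losses of 90% and 99%: the remainders are 0.010 and 0.009, so the first subset has weight 0.526 and the average is 0.36.
- Losses of 99% and 90%: the remainders are 0.001 and 0.090, and the average is 0.105.
- Equal losses: it stays at 0.15.

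No cell has changed in any of these cases. The shift, and its direction, depend on unequal loss or return of subsets.

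**Step 4: evaluability.** At a standardised difference of 0.497, power with 42.5 per arm is 63%. If 75%, 50% or 25% of SOCR samples are evaluable and all SOC samples are, it is 56%, 46% or 30%. These shares are illustrations. The selection in Step 3 is a question of bias, which a larger sample would not remove.

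**Step 5: mediation through the count.** With 1:1 arms whose means differ by k within-arm SDs, the squared correlation of arm and marker is k²/(k² + 4), so the variance inflation is 1 + k²/4. For k = 2, 4, 6 this is 2, 5, 10, and the standard error grows by 1.4, 2.2, 3.2. This is the linear-model result and only a guide for a logistic or Cox outcome model.

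**The case against.** The strongest reply is that depletion is the intended mechanism. The primary objective asks for the effect of SOCR versus SOC on the markers. That is a total effect, and a fall in B-lineage RNA through cell loss belongs to it. The protocol nowhere says that whole-blood results show expression per cell. This stands: for markers defined in every sampled patient the randomised contrast is valid, and only its reading is at issue.

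Second, cell number and composition are partly measured already. Counts exist at month 3, and flow cytometry observes composition directly, so a change in phenotype is a result being sought. This also stands, except for percentages among few residual cells, and for month 6, where no count is named.

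Third, cell thresholds and composition adjustment usually sit in an SAP or laboratory manual, and Section 7 leaves room for transformations and different regressions. Their absence here is therefore not the point. The point is what the protocol does fix: these markers, these visits, the visits at which counts are named, and mediation for every biomarker.

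A reader might infer stronger conclusions that the documents do not support:

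- That most SOCR ratios at months 3 and 6 will be unevaluable. Neither depth nor duration of depletion is given.
- That the whole primary objective would merely restate depletion. It also covers antibodies, histology and biopsy transcripts, and Section 3 says the study does not depend on the optional tubes.
- That the problem has gone by month 12. No time course of reconstitution is given, so month 12 cannot be presumed safe.

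**Conclusion.** The concern holds in a limited form. For the IL10/IL6 ratio and for subset percentages, the between-arm contrast is conditional on B-cell survival, which treatment alters in one arm. For B-lineage whole-blood transcripts, cell number alone can produce the contrast. Neither these contrasts nor a mediated share based on them shows a change in per-cell state or regulatory potential.

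The size runs from trivial to dominant. It turns on the depth and duration of depletion, the B-cell share of the transcript, and whether subsets are lost unequally, none of which the protocol states. Absolute counts, transcripts of little B-cell origin, and antibody and biopsy markers are largely or wholly outside the problem. It should be corrected before analysis, but it does not undermine the study.

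**What to change.** In Sections 3 and 7:

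1. Make absolute B-cell and subset counts, with zero as a valid value, the main between-arm B-cell marker at each visit where the planned samples give them. Specify the month-6 count. Section 3 lists four blood-sampling occasions but also speaks of three time points for each tube; settle this at the same time.
2. At every visit, analyse ratios and percentages only above a pre-set minimum B-cell number, report the evaluable share by arm, and label the contrast as conditional on B-cell survival.
3. Show B-lineage whole-blood contrasts unadjusted, as the total effect, and beside them adjusted for B-cell number where it is measured. Label the adjusted result descriptive, since it conditions on a post-treatment variable. Where the arms barely overlap on the count, it too is extrapolation.
4. Report no mediated proportion for a marker whose distributions in the two arms do not overlap.

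**Cost.** Mostly wording and a little more analysis, with fewer per-cell claims. The blood draws are already planned, but the protocol does not say whether the month-6 tubes yield an absolute count, so this must be confirmed before the change is called free.
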